8.4 CRITERIA FOR OFF-STUDY

Patients will be taken off study for the following:

- The patient voluntarily withdraws
- Death

Patients must be followed until all adverse events attributed to Descartes-30 have resolved to Grade 2. If an adverse event is not expected to resolve to Grade 2 or less, this will be noted in the patient medical record and the patient will be taken off-study.

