Patients diagnosed with ARDS or PNA will undergo screening during which informed consent will be obtained and eligibility assessed. Up to 7 or 14 days may elapse between confirmation of PNA or ARDS diagnosis respectively and administration of the first infusion of study product. Patients will be dosed once per day for 3 consecutive days (Day 0, 1, 2). In Arm 1 (Dose Escalation), patients were monitored for 7 days after the first Descartes-30 infusion (unless they are discharged from the administering unit prior to Day 7) with a safety review on Day 7 (or last day in the administering unit, whichever comes earlier) to determine whether the next patient in the trial can be dosed. In Arm 2 (Dose Expansion), patients will be enrolled consecutively to receive treatment on Day 0, 1, and 2 at a dose up to the MTD determined in Arm 1. For both Arms, there will be an optional visit on Days 14 and 21 and a mandatory visit on Day 28. Long-term follow-up will occur at Day 90 (in-person or telephone contact).

Study Intervention:

The study product will be manufactured from qualified allogeneic donors under GMP standards. After the product passes Quality Control, it will be shipped to the study site for storage. Patients will receive the first dose of Descartes-30 cells via intravenous administration within 14 days of diagnosis of ARDS or within 7 days of diagnosis of PNA. Patients will receive two more infusions over the following 2 days unless they meet the criteria for holding dose or discontinuing study treatment.

In the dose escalation arm (Arm 1), the following doses of Descartes-30 cells are planned:

- Dose Level 1: 100 million cells administered on Days 0, 1 and 2
- Dose Level 2: 300 million cells administered on Days 0, 1 and 2
- Dose Level 3: 600 million cells administered on Days 0, 1 and 2

- Dose Level 4: 1200 million cells administered on Days 0, 1 and 2

An additional 12 patients per cohort (ARDS or PNA) may be enrolled at a dose up to MTD.

Study Duration: 30 months

Participant Duration: 3 months

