8 SAFETY ASSESSMENT AND PROCEDURES

8.1 DEFINITIONS

8.1.1 ADVERSE EVENTS (AE)

An adverse event (AE) is defined as any reaction, side effect, or untoward event that occurs during the clinical trial associated with the use of a test article in humans, whether or not the event is considered related to the treatment or clinically significant. For this study, AEs will include events reported by the patient, as well as clinically significant abnormal findings on physical examination or laboratory evaluation. A new illness, symptom, sign or worsening of a pre-existing condition or abnormality is considered an AE. An abnormal laboratory value will be considered an AE if the laboratory abnormality is characterized by any of the following:

- Results in discontinuation from the study.
- Is associated with clinical signs or symptoms.
- Requires treatment or any other therapeutic intervention.
- Is associated with death or another serious adverse event, including hospitalization.
- Is judged by the Investigator to be of significant clinical impact.

All AEs, including clinically significant abnormal findings on laboratory evaluations, regardless of severity, will be followed until satisfactory resolution.

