8.2 RECORDING OF ADVERSE EVENTS

8.2.1 ADVERSE EVENT RECORDING

The adverse event recording period for this study starts after patient or legal representative signs consent and ends at Day 90 visit or when patient comes **off-study based on criteria in Section 8.4**. For SAE and SUSAR, reporting period starts with first Descartes-30 infusion and ends 7 days after last infusion. After 7 days, an AE (only in Arm 2), SAE (both Arms) or SUSAR (both Arms) is **only reported if it is probably or definitely attributed to Descartes-30 infusion**. At each contact with the subject during the adverse event recording period, the Investigator or his/her designee must seek information on adverse events by specific questioning and, as appropriate, by examination. Information on all adverse events should be recorded immediately in the source document, and in the appropriate adverse event module of the case report form (CRF). All clearly related signs, symptoms, and abnormal diagnostic procedures results should be recorded in the source document, though it should be grouped under one diagnosis.

All adverse events should be treated appropriately. If a concomitant medication or non-drug therapy is given, this action should be recorded on the Adverse Event CRF. Adverse events should be entered into the e-CRF system within 3 working days from the knowledge of the event took place. Once an adverse event is detected, it should be followed until its resolution or until it is judged to be permanent, and assessment should be made at each visit (or more frequently, if necessary) of any changes in severity, the suspected relationship to the study treatment, the interventions required to treat it, and the outcome.

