9.3 EFFICACY

Efficacy will be assessed by descriptive statistics of treatment response per clinical endpoints that are frequently used in ARDS outcome trials such as all-cause mortality at Day 28, change in SOFA score from baseline, change in WHO Ordinal Score, change in PaO₂ / FiO₂ ratio (arterial partial pressure of O₂ / fraction of inspired O₂) from 0 to 96 hours after first dose, to determine all-cause mortality at Day 28 for patients diagnosed with COVID-19, change in PaO₂ / FiO₂ ratio from 0 to 24, 48, and 96 hours after first dose, days free of renal support (for patients receiving renal support at baseline), days free of vasoactive support (for patients receiving at least one vasopressor at baseline), days free of mechanical ventilation, days with a fever (temperature $\geq 38^{\circ}\text{C}$) number of ICU-free days, and number of days in hospital.

Days free of mechanical ventilation is defined as the number of calendar days during which the patient is ventilator-free including two unassisted breathing (UAB) days to Day 28, assuming that a patient survives for at least two consecutive calendar days after initiating UAB.

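### The non-resolution clause in Section 8.4 has no time limit, so a patient with persistent product toxicity can leave adverse event recording before Day 28 or Day 90

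*Combined protocol and SAP*

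**What the plan says.** Section 8.4 (Criteria for Off-Study) lists two reasons for leaving the study: voluntary withdrawal and death. Two sentences follow the list. The first sets a duty to follow patients: "Patients must be followed until all adverse events attributed to Descartes-30 have resolved to Grade 2". The second is the clause at issue. It opens "If an adverse event is not expected to resolve to Grade 2 or less" and continues "this will be noted in the patient medical record and the patient will be taken off-study". It names no day before which it does not apply.

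Section 8.2.1 (Adverse Event Recording) starts the AE recording period at consent and says that it "ends at Day 90 visit or when patient comes" off-study, citing Section 8.4 for the criteria. The same section says of each detected event that "it should be followed until its resolution or until it is judged to be permanent".

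Section 8.1.1 (Adverse Events) says that all AEs, "regardless of severity, will be followed until satisfactory resolution".

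The Synopsis (Study Design) gives both arms "a mandatory visit on Day 28" and a Day 90 contact. Section 9.3 (Efficacy) lists "all-cause mortality at Day 28" among the descriptive outcomes, along with days free of ventilation, vasoactive and renal support and ICU-free days.

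**The concern.** Sections 8.4 and 8.2.1 are joined by an express cross-reference. A site that follows both would stop recording AEs for a patient once a persistent Descartes-30 toxicity is judged unlikely to improve to Grade 2, whatever the study day.

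Follow-up would then be cut short because of the toxicity itself. That is informative loss: the patients who leave are not a random subset, and descriptive tables built on those who remain would tend to understate what happens after a serious product reaction. The primary objective is a descriptive safety assessment, so the later course of these few patients carries much of the information the study is meant to produce. Stopping further infusions does not require leaving the study, because Section 7.1.2.5 defines off-treatment separately.

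**Working it through.** The plan gives no figure to reproduce: Section 9.1 states that no formal sample size calculation was done, and no removal or dropout rate appears. The check is a cross-reading, followed by simple bounds.

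**Step 1. Does the clause apply before Day 90?** It has no time restriction, so as written it does. It refers to an adverse event without saying attributed; that qualifier is carried over from the sentence before it. The narrower, attributed reading is used here.

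**Step 2. What stops?** AE recording stops, by the cross-reference in 8.2.1. Whether the Day 28 and Day 90 assessments stop is not stated, because off-study is not defined visit by visit.

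**Step 3. Does any other text keep these patients' outcomes?**
- Section 7.2.2.4 asks for reports after off-study, but only of malignancy or ectopic tissue.
- Section 10.5.3 seeks vital status, but only for subjects who revoke authorization to use their health information.
- Sections 8.3 and 8.3.1 require follow-up reports on an SAE already reported, with no off-study cut-off. These cover the course of that event, not the scheduled outcomes.
- Section 9 has no rule for missing outcomes.

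None of these retains Day 28 outcomes or Day 90 status.

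**Step 4. What is already captured?** Under Section 8.1.2, a Grade 3-5 toxicity probably or definitely attributed to Descartes-30 is a DLT. Section 4.5 counts it for escalation if it falls within 7 days of the first dose. The event precedes any judgment that it will not resolve, so the DLT is on record before the clause can operate. Grade 5 events lie outside the clause, since death is a separate off-study reason.

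**Step 5. How much later AE recording is at stake?** Under 8.2.1, after 7 days AEs in Arm 2 and SAEs in both arms are reported only if probably or definitely attributed. In Arm 2 the later loss is therefore of attributed events only. In Arm 1 it covers non-serious AEs more broadly.

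**Step 6. Effect on Day 28 mortality.** With n patients, d deaths observed and m patients of unknown status, the rate lies between d/n and (d + m)/n, a width of m/n. For a cohort of n = 12 (Section 4.5):
- m = 1: 1/12 = 8.3 percentage points
- m = 2: 2/12 = 16.7 points
- m = 3: 3/12 = 25.0 points

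Illustration with assumed counts: 2 of 12 removed before Day 28 and 3 deaths among the other 10. The complete-case rate is 3/10 = 30.0%; the rate in all 12 lies between 3/12 = 25.0% and 5/12 = 41.7%. With follow-up kept, status would be known for 12 of 12.

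**Step 7. How likely is at least one such removal?** For an assumed probability p per patient, the chance in a cohort of 12 is 1 - (1 - p)^12:
- p = 5%: 46%
- p = 10%: 72%
- p = 20%: 93%

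These rates are assumptions that show the range; nothing in the protocol supports one over another.

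**The case against.** The best counter-argument is contextual. The clause follows a duty to keep following patients and supplies the exit from it; non-resolution is not among the two listed off-study reasons. On that reading it only closes follow-up that would otherwise be open-ended, and nobody would be removed on it before Day 90. This is plausible and may be what was intended. It is not what the sentence says, and 8.2.1 refers to 8.4 without separating the listed reasons from the clause.

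Several stronger conclusions are tempting, and the documents do not support them.
- A reader might infer that the Day 28 and Day 90 visits are cancelled. No passage says so; the point is that none keeps them.
- A reader might infer that the MTD is compromised. The index toxicity is already a DLT, and Section 8.5 separately pauses the study for two related Grade 3 or 4 vital-organ events within 7 days of first infusion.
- A reader might infer that the outcome of the toxicity goes unrecorded. Where the event is an SAE, the follow-up reports in 8.3 and 8.3.1 continue.
- A reader might infer that an early exit forfeits nearly all of a 90-day AE record. Reporting is already restricted after 7 days, as Step 5 shows, and nothing indicates how early non-resolution would be judged.
- A reader might call 8.1.1 a flat contradiction. Satisfactory resolution is undefined there, so 8.2.1 and 8.4 could be read as specifying it. The three end-points still differ: satisfactory resolution, resolution or permanence, and Grade 2. Only the clause in 8.4 removes the patient; under 8.2.1 a judgment of permanence ends follow-up of the event alone.

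It is also fair that Day 28 mortality is a descriptive measure in a study without inferential aims. That limits the consequence, but a descriptive rate in 12 patients is sensitive to one unknown outcome.

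**Conclusion.** The point stands as a drafting gap with a real consequence if followed literally. As written, 8.4 with 8.2.1 allows toxicity-dependent exit from AE recording before Day 28 or Day 90, with nothing to secure the outcomes due at those times. The loss falls on later AEs, Day 28 all-cause mortality, the free-day endpoints and Day 90 status; the effect on the MTD is small.

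The size is conditional: up to 8.3 percentage points of uncertainty in Day 28 mortality per patient of unknown status in a cohort of 12. This rests on two assumptions. The first is that removal also ends outcome collection, which is inferred from the absence of any retaining text. The second is that removals occur before Day 28, at a rate the documents do not give. It should be corrected, but it does not undermine the dose-escalation design.

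**What to change.** In Section 8.4, state that the non-resolution clause only ends extended follow-up after the Day 90 visit. Add that, before then, such patients stay on study for AE recording, Day 28 outcomes and Day 90 vital status unless consent is withdrawn. Say explicitly that the clause concerns events attributed to Descartes-30, if that is the intent.

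Reconcile the related text: in 8.2.1, make the off-study end of AE recording match the revised 8.4; in 8.1.1, define satisfactory resolution so that it agrees with both.

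If anyone has already left under this clause, report the number and study day of removal, and give Day 28 mortality with the lower and upper bounds shown above.

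The cost is a sentence or two in 8.4 and matching edits in 8.2.1 and 8.1.1. No visits are added: Day 28 and Day 90 are already scheduled, and Day 90 may be done remotely.

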8.5 STUDY PAUSING AND STOPPING RULES

Premature termination of the clinical trial may occur because of a regulatory authority decision, change in opinion of the IRB or Medical Monitor. Additionally, recruitment may be stopped for reasons of particularly low recruitment, protocol violations, or inadequate data recording. Specifically, study will be stopped if:

- Study Sponsor or a Regulatory Body decides for any reason that subject safety may be compromised by continuing the study.
- The Sponsor decides to discontinue the development of the intervention to be used in this study.

The study will be **paused if:**

- There is death that is reasonably attributed to study product before Day 4.
- Two subjects with Grade 3 or 4 adverse events to vital organs that are assessed as probably or definitely related to study product within the first 7 days after first infusion.

If the study is paused for the reasons above, the PI and members of the study team will meet in person or by teleconference within 24 hours of the event to have a thorough discussion of the event. Meeting minutes capturing the review of any ongoing investigations, including next steps in the management of the subject and any proposed changes to the protocol will be forwarded to the Medical Monitor. If all parties agree as to the event resolution, then the pause will be lifted. If the study is paused for manufacturing reasons, the Sponsor will make recommendations for process improvements to be implemented. Pending successful completion of a process validation run, the manufacturing pause will be lifted.

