7.1.2 DOSING AND ADMINISTRATION

7.1.2.1 PRE-INFUSION MONITORING AND DELAY OF CELL INFUSION

[figure not shown]
Infusions can be delayed up to 96 hours based on PI discretion. Prior to all Descartes-30 infusions, patients should be observed for 2 hours (\pm 30 min) to document their stability by meeting the following parameters and based on PI's best clinical judgement:

1. Patient is not requiring a change in ventilator settings
2. Stable use of vasopressors if the patient required vasopressors for blood pressure support.
Stable use is defined as increasing no more than 50% of baseline recorded at initiation of monitoring.

During 2-hour monitoring, following parameters should be recorded at least every 30 min: ventilation variables [type of ventilation (CPAP, BiPAP, or intubation), ventilation rate, pulse, tidal volume, positive end-expiratory pressure (PEEP)], recording of vasoactive drugs and renal support and vital signs [include core temperature, mean arterial pressure (mmHg), pulse (beats/min), respiratory rate (breaths/min)]. If patients do not meet stability criteria for 2 hours, infusion can be delayed for up to 96 hours. If infusion is delayed, the patient will be periodically monitored to assess stability. If infusion is delayed more than 96 hours due to medical instability, patients will come off study treatment. Infusions can also be delayed up to 96 hours in case of a holiday or by PI's discretion.

Patients experiencing toxicities that are probably or definitely related to Descartes-30 will have their next Descartes-30 dose delayed until these toxicities have resolved to at least Grade 2, unless in the documented opinion of the site Principal Investigator and the medical monitor it is reasonable to proceed. During this period, patients will be assessed to record adverse events and decide whether the patient meets criteria for cell infusion. The discussions between the Medical Monitor and site Principal Investigator will be documented. If a dose is delayed for more than 96 hours, the patient will come off study treatment.

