7.2.2 MANAGEMENT OF TOXICITIES

The cellular base of Descartes-30 is MSCs, a cell type which has appeared safe for therapeutic use in prior studies including over 2000 patients.³⁹ Toxicities, if any, are expected to occur within several hours of MSC infusion. The largest dataset for guiding expectant toxicity management comes from a meta-analysis of 55 randomized clinical trials.³⁹ The MSC-secreted products are two human DNases that are normally present in serum; that are too bulky to enter cells; and for which the target (extracellular DNA) has no physiologic role in a healthy host. The expression of these DNases is therefore not expected to confer toxicity, although this hypothesis will be tested in this study in the usual cautious and regimented fashion. The guidelines below are recommendations only to manage these potential adverse events and can be tailored to an individual patient's needs based on the judgment of the Investigator or treating physician. Management that differs from these recommendations will not be considered a protocol deviation.

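### Section 8.5 lists no pause for a single product-attributed death on Day 4 or later, even one within hours of a delayed third infusion

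*Combined protocol and SAP*

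**What the plan says.** Section 8.5 (Study Pausing and Stopping Rules) has two event-based pause criteria:

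- Death: "There is death that is reasonably attributed to study product before Day 4".
- Non-fatal toxicity: "Two subjects with Grade 3 or 4 adverse events to vital organs that are assessed as probably or definitely related" to the product, within the first 7 days after first infusion.

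After a pause, the investigator and study team "will meet in person or by teleconference within 24 hours of the event". The pause ends when all parties agree that the event is resolved.

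Infusions are planned for Days 0, 1 and 2. Section 7.1.2.1 allows a delay of up to 96 hours for instability, for related toxicity or at the investigator's discretion. It adds: "Infusions can also be delayed up to 96 hours in case of a holiday".

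On timing of harm, 7.2.2 states: "Toxicities, if any, are expected to occur within several hours of MSC infusion". Section 8.1.2 lists death within 4 hours of an infusion as a dose-limiting toxicity (DLT). Section 8.2.1 sets the reporting window from the last infusion: "For SAE and SUSAR, reporting period starts with first Descartes-30 infusion and ends 7 days after last infusion".

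For Arm 2, the synopsis says "patients will be enrolled consecutively to receive treatment on Day 0, 1, and 2 at a dose up to the MTD". The minimum 7-day spacing between patients in 4.4 applies to the escalation arm only.

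**The concern.** A pause rule should respond at least as firmly to a death as to a less severe event. Here the death criterion closes after Day 3, while the non-fatal criterion stays open for 7 days from first infusion. The protocol gives no reason for the shorter window. Section 4.4 justifies the Day 7 safety review by DNase expression that wanes over 7 days, which argues against it.

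The death cut-off is also fixed to Day 0, whereas the expected toxicity follows each infusion. A permitted delay can move the last infusion, or the last two, past the cut-off altogether.

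At stake is whether other patients' dosing stops automatically after a related death or only if someone decides to stop it. This matters most in Arm 2, planned for up to 24 patients (4.2) with no stated stagger, where several patients may be mid-course when a death occurs.

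**Working it through.** There is no operating characteristic to reproduce: section 9.1 says no formal sample size calculation was made. The check applies the rule text and counts days.

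**Inputs.** Day 0 is the first infusion, and infusions are planned on Days 0, 1 and 2 (synopsis, 4.3). The maximum delay is 96 hours (7.1.2.1). Criterion 1 covers Days 0 to 3 (8.5). Criterion 2 needs two subjects, Grade 3 or 4, within 7 days of first infusion (8.5). The serious adverse event (SAE) period ends 7 days after the last infusion (8.2.1).

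**Step 1: apply both criteria to four cases.**

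| Case | Criterion 1 | Criterion 2 | Listed pause? |
|---|---|---|---|
| One attributed death, Day 3 | Met | Not met | Yes |
| One attributed death, Day 6 | Too late | One subject only | No |
| Two subjects with related Grade 3 vital-organ events, Day 6 | Not a death | Met | Yes |
| One attributed death within 4 hours of a third infusion given on Day 4 | Too late | One subject only | No |

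**Step 2: delay before the third infusion.** With h the delay in hours, third infusion day = 2 + h/24. Calendar days from that infusion still inside criterion 1, counting the infusion day, = max(0, 4 − third infusion day). End of the SAE period = third infusion day + 7.

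| Delay (h) | Third infusion | Days still covered | SAE period ends |
|---|---|---|---|
| 0 | 2 + 0 = Day 2 | 4 − 2 = 2 | Day 9 |
| 24 | 2 + 1 = Day 3 | 4 − 3 = 1 | Day 10 |
| 48 | 2 + 2 = Day 4 | 0 | Day 11 |
| 72 | 2 + 3 = Day 5 | 0 | Day 12 |
| 96 | 2 + 4 = Day 6 | 0 | Day 13 |

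**Step 3: delay before the second infusion, with the third a day later.** Second infusion day = 1 + h/24; third = 2 + h/24.

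- 48 h: Days 3 and 4, so one infusion is outside criterion 1.
- 72 h: Days 4 and 5, so two are outside.
- 96 h: Days 5 and 6, so two are outside.

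**Step 4: both delayed.** Section 7.1.2.1 words the limit by dose. If it applies separately to each, two 96-hour delays put the second infusion on Day 1 + 4 = 5 and the third on Day 5 + 1 + 4 = 10. The main result does not need this reading.

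**The case against.** The strongest reply is that new patients are not dosed by default. In Arm 1, first infusions are at least 7 days apart, and the next patient is authorised only if the review finds no safety concern (4.4). A known related death would plainly fail that check. In Arm 2, the Medical Monitor must approve each enrollment on cumulative data (4.5). SAEs reach the sponsor within 24 hours (8.3.1), and the sponsor or a regulator can stop the study for safety, as can a change in opinion of the IRB or Medical Monitor (8.5). This largely stands. A reader might infer that recruitment would run on unchecked after a late related death; the documents do not support that. What remains is reliance on judgement where 8.5 otherwise sets a rule, and the remaining infusions, at most two each, of Arm 2 patients who have already started. Approval at enrollment does not reach those infusions.

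Second, on schedule, Days 0 to 3 include all three infusions and the day after the last. That also stands: the acute form of the gap needs a delay totalling 48 hours or more. Counting uncovered days as a share of the SAE period would exaggerate it, because risk is not expected to be equal across days.

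Third, because 7.1.2.1 says patients with related toxicity "will have their next Descartes-30 dose delayed until these toxicities have resolved to at least Grade 2", a reader might infer that those outside the criterion are mainly patients already harmed by the product. That does not follow. Related Grade 3 or higher toxicity is a DLT under 8.1.2, and 7.1.2.5 takes patients with a directly attributable DLT off treatment. Those delayed for instability must first show about 2 hours of stability. Other delays are for holidays or discretion.

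**Conclusion.** The gap is real on the text. A single death attributed to the product on Day 4 or later triggers no listed pause, while a less severe pattern inside 7 days does. Any delay of 48 hours or more before the third infusion leaves none of the period after that infusion under the death criterion.

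Two further inferences go too far. A reader might conclude that even two late related deaths could not pause the study. Criterion 2 does not name Grade 5, but each such patient could count towards it if a related Grade 3 or 4 vital-organ event was recorded within 7 days of first infusion, so the flat statement fails. A reader might also infer, from the differing wording of 4.5 and 8.1.2, that a countable DLT is undefined. Carrying the 4.5 relatedness and 7-day conditions forward is the natural reading, and the synopsis describes Arm 1 monitoring in the past tense. Nothing here rests on that comparison.

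The size is given in days and infusions, not as a probability: the documents give no rate of delays or related deaths, and do not say how many of the 24 Arm 2 patients are still to be treated. The conclusion assumes that study days run from the first infusion without renumbering after a delay, and that a pause holds infusions in patients mid-course. Section 8.5 does not spell out the latter.

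**What to change.** Replace the first pause bullet in 8.5 with: *any death reasonably attributed to study product, at any time on study, in either arm*. The minimum alternative is to run the criterion through 7 days after the last infusion actually given, matching 8.2.1. That window would end on Day 9 on schedule and on Day 11, 12 or 13 after a 48-, 72- or 96-hour delay. It would help to state that the pause covers remaining infusions in patients already being treated.

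The change costs one line of protocol text and an occasional short pause. Because the trigger requires attribution to the product, deaths from the underlying illness would not fire it. The existing 24-hour meeting and the lifting of the pause on agreement would apply unchanged.
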